4.2 End of Study

The end of the study is defined as the date of the last visit of the last patient undergoing the trial.

4.3.3 Azacitidine

Chemical Name: 4-amino-1- β -D-ribofuranosyl-s-triazin-2(1H)-one

Formulation, preparation, storage and stability: Please see commercial package insert approved by regulatory agencies⁵⁶.

Route of Administration: Subcutaneous injection, or IV infusion for 7 consecutive days (Days 1-7). Subcutaneous route is preferred but IV administration is acceptable at the Investigator's discretion. The same route should be maintained over the 7-day treatment period.

4.4 Duration of Therapy

Patients may remain on study treatment to the end of the trial while deriving clinical benefit, unless unacceptable toxicity, progression, death or patient withdrawal requires discontinuation. For patients without disease progression or unacceptable toxicity, study treatment should proceed for a minimum of 6 months to allow time for clinical response. Patients may remain on protocol therapy after relapse or progression if they are continuing to derive clinical benefit in the opinion of the Investigator.

4.5 Trial Discontinuation

For reasonable cause, either the Investigator or the Sponsor may terminate this study prematurely. Written notification of the termination is required. Conditions that may warrant termination include, but are not limited to:

- The discovery of an unexpected, significant, or unacceptable risk to the patients enrolled in the study.
- Failure of the Investigator to enter patients at an acceptable rate.
- Insufficient adherence to protocol requirements (non-compliance).
- Lack of evaluable and/or complete data.
- Decision to modify the developmental plan of the drug.
- A decision on the part of the Sponsor to suspend or discontinue development of the drug.

4.6 Drug Accountability/Disposition of Clinical Trial Supplies

Drug accountability records will be maintained for all clinical trial supplies.

All unused clinical trial supplies will be destroyed per the institution's standard operating procedure. Destruction of drug and trial supplies must be documented, and the documentation will be reviewed by/sent to the Sponsor or their Designee.

4.7 Registration

Prior to registration and any study-specific evaluations being performed, all patients must have given written informed consent for the study and must have completed the pre-study evaluations (see Section 7.1). Patients must meet all of the eligibility requirements listed in Section 5.0. Patients will be registered on the study by using the [REDACTED] Interactive Web Response System (IWRs) automated patient registration system.

5.0 SELECTION AND WITHDRAWAL OF PATIENTS

5.1 Inclusion Criteria for Patients in Safety Lead-In Cohorts

1. Signed ICF and ability to comply with protocol requirements.
2. Documented diagnosis of initial or relapsed AML according to World Health Organization (WHO) classification.
3. Adequate organ function as defined by the following laboratory values:
 - a. Creatinine clearance >30 mL/min (by Cockcroft-Gault method; [APPENDIX II](#)),
 - b. Total serum bilirubin $<1.5 \times$ ULN unless due to Gilbert's syndrome, leukemic organ involvement, hemolysis or considered an effect of regular blood transfusions,
 - c. ALT and AST $<3 \times$ ULN, unless due to leukemic organ involvement.
4. Age ≥ 18 years at the time of signing the ICF.
5. At least one *TP53* mutation which is not benign or likely benign.
6. ECOG performance status of 0, 1 or 2 ([APPENDIX III](#)).
7. Projected life expectancy of ≥ 12 weeks.
8. Negative serum or urine pregnancy test prior to study treatment initiation in female patients of childbearing potential.
9. Females of childbearing potential and males with female partners of childbearing potential must be willing to use an effective form of contraception such as latex condom, hormonal birth control, intrauterine device or double barrier method ([APPENDIX IV](#)) during chemotherapy treatment and for at least six months thereafter.

5.2 Exclusion Criteria for Patients in Safety Lead-In Cohorts

1. Prior treatment for *TP53*-mutant AML not permitted per [Table 3](#).
2. Known history of HIV or active hepatitis B or active hepatitis C infection.
3. Any of the following cardiac abnormalities:
 - a. Myocardial infarction within six months prior to registration,
 - b. New York Heart Association Class III or IV ([APPENDIX V](#)) heart failure or known LVEF $<40\%$;
 - c. A history of familial long QT syndrome,
 - d. Symptomatic atrial or ventricular arrhythmias not controlled by medications,
 - e. QTcF ≥ 470 msec, unless due to underlying bundle branch block and/or pacemaker and with approval of the Medical Monitor.
4. Concomitant malignancies for which patients are receiving active therapy at the time of signing consent. For example, patients with adequately treated basal or squamous cell carcinoma of the skin, adequately treated carcinoma *in situ* (e.g. cervix), or breast cancer

receiving adjuvant endocrine therapy may enroll irrespective of the time of diagnosis with Medical Monitor approval.

5. Known active CNS involvement from AML. A diagnostic lumbar puncture is not required in the absence of suspicion for CNS disease.
6. Malabsorption syndrome or other condition that precludes enteral route of administration.
7. Pregnancy or lactation.
8. Active uncontrolled systemic infection (viral, bacterial or fungal).

5.3 Inclusion Criteria for Patients in Expansion Cohorts

1. Signed ICF and ability to comply with protocol requirements.
2. Newly diagnosed or R/R AML according to WHO classification with permitted prior therapy, as per [Table 3](#). For patients with newly diagnosed AML bone marrow and/or blood evidence of AML with $\geq 20\%$ blasts is required. For patients with newly diagnosed AML, prior therapy with HMA and/or any chemotherapeutic agent for MDS is excluded.
3. Adequate organ function as defined by the following laboratory values:
 - a. Creatinine clearance > 30 mL/min (by Cockcroft-Gault method; [APPENDIX II](#)),
 - b. Total serum bilirubin $< 1.5 \times$ ULN unless due to Gilbert's syndrome, leukemic organ involvement, hemolysis or considered an effect of regular blood transfusions,
 - c. ALT and AST $< 3 \times$ ULN, unless due to leukemic organ involvement.
4. Age ≥ 18 years at the time of signing the ICF.
5. At least one *TP53* mutation which is not benign or likely benign, based on central *TP53* testing results. If local *TP53* mutation and/or p53 IHC results become available before central *TP53* mutation results, enrollment may be made based on local results with Medical Monitor approval.
6. ECOG performance status of 0, 1 or 2 ([APPENDIX III](#)).
7. Projected life expectancy of ≥ 12 weeks.
8. Negative serum or urine pregnancy test prior to study treatment initiation in female patients of childbearing potential.
9. Females of childbearing potential and males with female partners of childbearing potential must be willing to use an effective form of contraception such as latex condom, hormonal birth control, intrauterine device or double barrier method ([APPENDIX IV](#)) during chemotherapy treatment and for at least six months thereafter.

5.4 Exclusion Criteria for Patients in Expansion Cohorts

1. Known history of MPN (i.e., polycythemia vera, essential thrombocythemia and primary myelofibrosis are excluded).
2. Known history of HIV or active hepatitis B or active hepatitis C infection.
3. Any of the following cardiac abnormalities:
 - a. Myocardial infarction within six months prior to registration,

- b. New York Heart Association Class III or IV ([APPENDIX V](#)) heart failure or known LVEF <40%,
- c. A history of familial long QT syndrome,
- d. Symptomatic atrial or ventricular arrhythmias not controlled by medications,
- e. QTc \geq 470 msec calculated from a mean of 3 ECG readings using Fridericia's correction (QTcF = QT/RR^{0.33}).
4. Concomitant malignancies for which patients are receiving active therapy at the time of signing consent. For example, patients with adequately resected basal or squamous cell carcinoma of the skin, adequately resected carcinoma *in situ* (e.g. cervix), or breast cancer receiving adjuvant endocrine therapy may enroll irrespective of the time of diagnosis with Medical Monitor approval.
5. Prior exposure to anticancer therapies including chemotherapy, radiotherapy or other investigational therapy, including targeted small molecule agents within 14 days of the first day of study drug treatment or within 5 half-lives prior to first dose of study drug.
6. Prior exposure to biologic agents (e.g. monoclonal antibodies) for anti-neoplastic intent within 14 days prior to first dose of study drug.
7. Known active CNS involvement from AML. A diagnostic lumbar puncture is not required in the absence of suspicion for CNS disease.
8. Malabsorption syndrome or other condition that precludes enteral route of administration.
9. Pregnancy or lactation.
10. Active uncontrolled systemic infection (viral, bacterial or fungal).

5.5 Inclusion of Women, Minorities and Children

Both men and women and members of all races and ethnic groups are eligible for this study. Children are not eligible for this study because the safety and tolerability of the proposed dosing schedule has not been determined in adults.

5.6 Withdrawal Criteria

Protocol therapy can continue for patients receiving clinical benefit, unless one or more study treatment discontinuation criteria are met, or at the patient's discretion, or if the study is terminated.

5.6.1 Study Treatment Discontinuation

Study treatment must be discontinued if:

- Evidence of disease progression. Patients who have relapsed or progressive disease but who are continuing to derive clinical benefit in the opinion of the investigator may continue to receive study treatment.

- A patient becomes pregnant.
- A patient is significantly non-compliant with the requirements of the protocol.
- A patient has an adverse experience that would, in the Investigator's judgment, make continued participation in the study an unacceptable risk.
- The patient starts new treatment for their underlying disease.

5.6.2 Study Completion

Patient must be taken off the study if:

- The patient dies during the study.
- The patient is lost to follow-up.
- The patient withdraws consent.

5.6.3 Withdrawn Patients

When a patient is removed from the study treatment, the Investigator will clearly document the reason in the medical record and complete the appropriate CRF page describing the reason for discontinuation. In addition, every effort should be made to complete the appropriate assessments listed in Section 7.3.

5.7 Noncompliance

All instances of protocol deviations will be recorded according to guidelines per Sponsor's Representative.

6.0 TREATMENT OF PATIENTS

6.1 Drug Preparation and Administration

Study treatment may be administered on an outpatient basis. No investigational or commercial agents or therapies other than those described below may be administered with the intent to treat the patient's disease.

6.1.1 APR-246

APR-246 is administered as a 6-hour IV infusion daily on Days 1–4 of each 28-day cycle. APR-246 fixed dose is 4.5 g. APR-246 is administered in a 2-step infusion:

Step 1: Loading dose of 1.5 g for the first 45 minutes (\pm 2 min)

Step 2: Maintenance dose of 3 g over 5 hours 15 minutes (\pm 30 min)

In each portion of the study, if patients develop intolerable toxicity(ies) to APR-246 in combination with venetoclax and azacitidine, the dose of APR-246 may be reduced (please consult Section 4.1 and [Table 2](#)).

APR-246 vials are to be stored at 2-8°C (35.6-46.4°F). At the pharmacies and at the study centers, the prepared APR-246 study product (diluted in sodium chloride solution) is to be stored at not more than 25°C. The infusion should be completed within 24 hours from the time of preparation.

Detailed instructions on vial concentration, preparation and dispensing can be found in the Pharmacy Binder. The infusion timing, including start/stop times and the time of rate change, must be recorded.

6.1.2 Venetoclax

After ramp-up (see below), venetoclax tablets at the dose 400 mg (4 tablets) should be taken orally once daily with a meal and water, at approximately the same time every day. On days 1-4 of Cycle 1 it is recommended that venetoclax is taken approximately one hour after start of APR-246 infusion. On these days' patients will consume a low-fat meal prior to venetoclax consumption. Starting at cycle 2 venetoclax can be taken before or after start of APR-246 infusion (\pm 2 hours).

During Cycle 1, treatment with venetoclax should start with a ramp-up phase. If no prophylactic antifungal agent is administered concurrently, the ramp-up phase should consist of 100, 200, and 400 mg of venetoclax once daily given on days 1, 2, and 3 of Cycle 1, respectively. For day 4 of Cycle 1 and beyond, the venetoclax dose is 400 mg once daily given in combination with APR-246 with and without azacitidine. If a prophylactic antifungal agent is administered concurrently, the ramp-up and maintenance dose of venetoclax should be determined based on institutional practice and current prescribing information for venetoclax (please see [APPENDIX VIII](#)).

If required, any dosage modifications of venetoclax should be done based on clinical judgement and institutional practice.

Detailed instructions on preparation and administration can be found in the Pharmacy Binder and current package insert.

6.1.3 Azacitidine

Azacitidine is given at the standard dose of 75 mg/m² subcutaneously or intravenously over 7 consecutive days, Days 1-7. On Days 1-4 azacitidine is administered immediately after the APR-246 infusion. SC method is preferred but IV is allowed at the Investigator's discretion. The same route should be maintained over the 7-day treatment period (whichever route is used on Day 1, the other days should follow the same route of administration). Detailed

instructions on preparation and administration can be found in the Pharmacy Binder, current package insert, and in Section [6.2](#), below. The administration of azacitidine may be interrupted by up to 3 days to account for institutional administration practices and policies in addition to holidays.

6.1.3.1 Administration on the Days of PK Blood Sampling

On Cycle 1 Day 1, in subjects receiving APR-246 in combination with venetoclax and azacitidine, APR-246 is the first agent to be administered after the baseline blood sample for PK analysis is collected. Fifteen (15) minutes after the start of the infusion, the subject is asked to have breakfast. One (1) hour after the start of APR-246, the subject is to take venetoclax. Azacitidine is to be administered after the infusion of APR-246.

After C1, venetoclax can be taken before or after start of APR-246 (± 2 hrs) and after the baseline PK sample is obtained, as indicated in the [Schedule of Study Evaluations](#).

On Day 1 of Cycle 1 patients will come to the clinic for PK blood sampling without taking the venetoclax in the morning. Patients will receive a low-fat meal and take the venetoclax within 30 min after the meal is finished and a baseline blood sample is taken.

6.1.4 Dose-Limiting Toxicity

An event will be considered a DLT per NCI CTCAE version 5.0 criteria if it occurs within 4-week safety assessment period (Cycle 1 of study treatment) and meets at least one of the criteria below:

- Absolute neutrophil count (ANC) not recovering to $>0.5 \times 10^9/L$ and/or platelets not recovering to $>25 \times 10^9/L$ by day 42 of study treatment in the absence of active leukemia/myelodysplasia;
- Grade ≥ 3 nausea/vomiting/diarrhea or CNS toxicity that does not resolve to Grade ≤ 1 within 7 days despite treatment interruption and maximum medical therapy;
- Treatment-related non-hematological Grade ≥ 3 toxicity that does not resolve to Grade ≤ 1 .

A DLT will be considered related to the study treatment unless there is a clear, alternative explanation for the AE. A \geq Grade 3 metabolic or electrolyte abnormalities that is not clinically significant and is adequately controlled within 72 hours is not to be considered DLT. A tumor lysis syndrome that responds to therapy and resolves within 72 hours is not to be considered DLT.

Additionally, AEs that meet the above criteria, but occur after the DLT evaluation period will not be defined as DLTs, but will be reported as AEs/Serious Adverse Events (SAEs) and will be reviewed across all cohorts during the study to help determine the AE profile. A patient

that discontinues therapy during Cycle 1 without DLT is considered evaluable for the purpose of safety only if at least 80% of doses of APR-246 in combination with venetoclax with and without azacitidine were administered in the first cycle.

Patients who are tolerating APR-246 in combination with venetoclax and/or azacitidine, will not have to discontinue dosing prematurely due to the occurrence of DLTs in another patient in the same cohort, unless decided by the DRT. If requested by the Investigator, depending on the nature of the DLT and patient status, the DRT and the Sponsor may allow a patient to continue with study treatment at a reduced dose.

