Dose-finding study design will be applied to each cohort of the safety lead-in portion ([Figure 1](#)). Each cohort will enroll up to a maximum of 6 patients. Dose-limiting toxicity (DLT) will be assessed after three patients have been enrolled in respective cohort and the last enrolled patient has completed the 4-week safety assessment period (i.e., one cycle of combination regimen). A patient that discontinues therapy during Cycle 1 without DLT is considered evaluable for the purpose of safety only if at least 80% of scheduled doses of APR-246 in combination with venetoclax with and without azacitidine were administered in the first cycle. At the first dose level of 4.5 g/day of APR-246, if ≤1 patient out of 3 experiences a DLT, 3 additional patients will be enrolled. If ≤1 patient out of 6 experiences DLT, the dose level (4.5 g/day of APR-246) will be deemed the recommended Phase II dose (RP2D) for that cohort. If ≥2 patients out of the total 3 – 6 patients in the cohort experience DLT, the study will

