Statistics	
This is a Phase I, open-label, dose-finding and cohort expansion study to determine the safety and preliminary efficacy of APR-246 in combination with venetoclax and/or azacitidine in patients with AML.
 
The RP2D of APR-246 will be defined as the dose at which <2 out of 6 patients experience DLT during the 4-week safety assessment period after administration of APR-246 in combination with venetoclax and/or azacitidine.
 
Definition of Dose-Limiting Toxicity (DLT)
 
An event will be considered a DLT per NCI CTCAE version 5.0 criteria if it occurs within the 4-week safety assessment period (Cycle 1 of study treatment) and is not attributable to the underlying disease. DLT is defined as:
 
• Absolute neutrophil count (ANC) not recovering to $>0.5 \times 10^9/L$ and/or platelets not recovering to $>25 \times 10^9/L$ by day 42 of study treatment in the absence of active leukemia or myelodysplasia;• Grade ≥ 3 nausea/vomiting/diarrhea or CNS toxicity that does not resolve to Grade ≤ 1 within 7 days despite treatment interruption and/or maximal medical therapy;• Treatment-related non-hematological Grade ≥ 3 toxicity that does not resolve to Grade ≤ 1. 
A DLT will be considered related to the study treatment unless there is a clear, alternative explanation for the AE. A \geq Grade 3 metabolic or electrolyte abnormalities that is not clinically significant and is adequately controlled within 72 hours is not to be considered DLT. Tumor lysis syndrome (TLS) that responds to therapy and resolves within 72 hours is not considered DLT.
 
Additionally, AEs that meet the above criteria, but occur after the DLT evaluation period will not be defined as DLTs, but will be reported as AEs/Serious Adverse Events (SAEs) and will be reviewed across all cohorts during the study to help determine the AE profile. A patient that discontinues therapy during Cycle 1 without DLT is considered evaluable for the purpose of safety only if at least 80% of scheduled Cycle 1 dose of APR-246 in combination with venetoclax and/or azacitidine were administered in the first cycle.

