Each cohort will enroll up to 6 patients. DLT will be assessed after three patients have been enrolled in respective cohort and the last enrolled patient has completed the 4-week safety assessment period (i.e., one cycle of combination regimen). A patient that discontinues therapy during Cycle 1 without DLT is considered evaluable for the purpose of safety only if at least 80% of scheduled doses of APR-246 in combination with venetoclax and/or azacitidine were administered in the first cycle. At the first dose level of 4.5 g/day of APR-246, if ≤1 patient out of 3 experiences a DLT, 3 additional patients will be enrolled. If ≤1 patient out of 6 experiences DLT, the dose level (4.5 g/day of APR-246) will be deemed the RP2D for that cohort. If ≥2 patients out of the total 3–6 patients in the cohort experience DLT, the study will continue enrollment at Dose Level -1 (4.0 g/day of APR-246). If ≤1 patient out of 6 experiences DLT at this dose level, the dose level (4.0 g/day of APR-246) will be deemed the

RP2D for that cohort. If ≥ 2 patients out of the total 3 – 6 patients at that dose level experience DLT, the study will continue enrollment at Dose Level -2 (3.5 g/day of APR-246). If ≤ 1 patient out of 6 experiences DLT at this dose level, the dose level (3.5 g/day of APR-246) will be deemed the RP2D for that cohort. If ≥ 2 patients out of the total 3–6 patients at this dose level experience DLT, no additional patients will be enrolled at this dose. The trial will be halted, and the DRT will consider potential future dosing modifications.

Table 2. APR-246 Dose Levels

Dose Modification	APR-246 Dose
Starting Dose Level (DL)	APR-246 4.5 g/day 1.5 g (for first 45 minutes) + 3.0 g (for 5 hours 15 minutes)
Dose Level Reduction -1 (DL-1)	APR-246 4.0 g/day 1.33 g (for first 45 minutes) + 2.67 g (for 5 hours 15 minutes)
Dose Level Reduction -2 (DL-2)	APR-246 3.5 g/day 1.17 g (for first 45 minutes) + 2.33 g (for 5 hours 15 minutes)

The expansion portion will begin once the RP2D of APR-246 in combination with venetoclax and/or azacitidine have been determined in order to assess the antitumor activity of these combinations. Approximately 70 patients will be enrolled in up to five cohorts, as outlined in [Table 3](#):

Table 3. Study Treatment and Prior Therapy by Cohort

Cohort	Disease	Study Treatment	Prior Therapy Permitted						
			VEN	HMA	LDAC	APR-246	SCT	IC	
Safety Lead-In Cohorts									

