6.1.5 Recommended Phase II Dose (RP2D)

The RP2D of APR-246 will be defined as the dose at which <2 out of 6 patients experience DLT during the 4-week safety assessment period after administration of APR-246 in combination with venetoclax and/or azacitidine.

DRT consisting of the Medical Monitor, Site Principal Investigators, and other clinical research personnel that the Sponsor may deem appropriate, will hold DRM on an interim basis at a frequency dependent on study accrual. At these meetings, the DRT will review AEs and DLTs and make recommendations regarding the RP2D. In the expansion portion of the study, the DRT will evaluate safety and tolerability after 5 patients have completed 1 cycle of treatment in each cohort. All accumulated safety data will be discussed during DRMs.

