9.2 Analysis Populations

Safety population: Patients will be evaluable for safety if they receive at least one dose of APR-246 with venetoclax and/or azacitidine. The safety population will be used to summarize exposure and safety parameters.

DLT-evaluable population: All patients who either experienced a DLT during first 4 weeks (Cycle 1) of the study treatment or received $\geq 80\%$ of scheduled Cycle 1 dose of APR-246 in combination with venetoclax and/or azacitidine and did not experience a DLT. Any individual patient who is not evaluable for DLT will be replaced by a new patient through additional patient enrollment.

Efficacy evaluable (EE) population: All patients who complete at least one treatment cycle of APR-246 in combination with venetoclax and/or azacitidine and who have at least one post-treatment clinical response assessment. Patients who fail to complete one treatment cycle will also be considered EE if they show clear evidence of clinically significant disease progression. The EE population will be the secondary analysis population for efficacy.

Pharmacokinetics (PK) population: Patients will be evaluable for pharmacokinetics if at least one post-dose sample for PK evaluation has been obtained.

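### DLTs are counted only within the 4-week Cycle 1 period, but the only haematological DLT criterion is judged at Day 42, and neither the RP2D rule nor the DLT-evaluable set requires Day 42 status

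*Combined protocol and SAP*

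**What the plan says.** **Window.** Section 6.1.4 makes an event a DLT "if it occurs within 4-week safety assessment period (Cycle 1 of study treatment") and it meets at least one of three criteria. The synopsis (Statistics) sets the same limit: "if it occurs within the 4-week safety assessment period (Cycle 1 of study treatment"). Section 6.1.4 adds that qualifying events that "occur after the DLT evaluation period will not be defined as DLTs"; they are reported as AEs or SAEs and reviewed across cohorts.

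**Haematological criterion.** Only one criterion covers blood counts: ANC not recovering to >0.5 × 10⁹/L and/or platelets not recovering to >25 × 10⁹/L "by day 42 of study treatment in the absence of active leukemia/myelodysplasia". The third criterion is limited to non-haematological toxicity, so it cannot pick up cytopenia.

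**Rules that use the count.**
- Review trigger (4.1 and synopsis): DLT "will be assessed after three patients have been enrolled in respective cohort" and "the last enrolled patient has completed the 4-week safety assessment period".
- RP2D (6.1.5): the dose at which fewer than 2 of 6 "patients experience DLT during the 4-week safety assessment period after administration of APR-246" in combination. Section 9.3.1 repeats this as a primary endpoint.
- DLT-evaluable population (9.2): patients who "experienced a DLT during first 4 weeks (Cycle 1) of the study treatment", or who received at least 80% of the scheduled Cycle 1 dose without a DLT.

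**Reported outcome.** The synopsis (Study Design) says that six patients in each lead-in cohort, each with one cycle or more of treatment, were reviewed. No DLTs were found, and the RP2D was set at 4.5 g/day for both combinations. The meetings were on 27 February and 26 June 2020 (Cohort 2) and on 17 March and 7 August 2020 (Cohort 1).

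**The concern.** A criterion that is read at Day 42 cannot be settled by a rule that closes at Day 28. Under Section 9.2, a patient who is still cytopenic at the end of Cycle 1 but has taken enough drug enters the DLT-evaluable set as DLT-free. Section 6.1.5 can then count that patient towards the fewer-than-2-of-6 rule. Neither section asks for Day 42 status.

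DLTs and the RP2D are primary endpoints, and the RP2D sets the dose for an expansion portion of approximately 70 patients. What is at stake is whether 0 of 6 in each cohort is complete on its only haematological component. Safety reporting as a whole is not at stake, because late cytopenia is still recorded as an AE.

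**Working it through.** **1. The plan's own figure.** The lead-in size reproduces: 2 cohorts × 6 patients × 1 dose level = 12, and 2 × 6 × 3 dose levels = 36, as in Section 9.1. The decision unit is therefore six patients per dose level, accepted at 0 or 1 DLT.

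**2. The gap.** 42 − 28 = 14 days between the end of the counting period and the reading of the haematological criterion.

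**3. Does any rule wait for Day 42?**

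| Rule | Section | Period used | Day 42 required? |
|---|---|---|---|
| DLT must occur | 6.1.4, synopsis | 4 weeks | Only inside the haematological criterion |
| Review trigger | 4.1, synopsis | 4 weeks; explicit only for the first three patients | No |
| RP2D | 6.1.5, 9.3.1 | 4-week safety assessment period | No |
| DLT-evaluable | 9.2 | 4 weeks, or ≥80% of Cycle 1 dose | No |

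**4. Was Day 42 known at the RP2D reviews?** Count the first dose as Day 1. For a review on date T, the latest start that has reached Day 28 is T − 27 days, and the latest that has reached Day 42 is T − 41 days.

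| | Cohort 2 | Cohort 1 |
|---|---|---|
| First review | 27 Feb 2020 | 17 Mar 2020 |
| Second review | 26 Jun 2020 | 7 Aug 2020 |
| Interval | 120 days | 143 days |
| Patients 1-3: study day at second review, at least | 28 + 120 = 148 | 28 + 143 = 171 |
| Patients 4-6: latest start with Day 28 reached | 30 May | 11 Jul |
| Patients 4-6: latest start with Day 42 reached | 16 May | 27 Jun |
| Starts with Day 28 reached but Day 42 pending | 17-30 May | 28 Jun-11 Jul |

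The line for patients 1-3 assumes that they had completed Day 28 at the first review, as the trigger requires. For them the question is closed. For patients 4-6 it is open only for someone who started within the last row's dates. Start dates are not given and accrual is unknown, so these ranges cannot be turned into a probability.

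**5. Effect on the rule.** Starting from 0 of 6, one unrecovered patient gives 1 of 6, and the dose is still accepted. Two give 2 of 6, and it is not. One late failure would change the reported count; at least two in the same cohort would be needed to change the RP2D.

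**The case against.** The strongest reply is that the text does not conflict. Section 6.1.4 has two conditions: the event occurs within 4 weeks, and it meets a criterion. Four weeks governs onset, and Day 42 belongs to the criterion. The gastrointestinal/CNS criterion works the same way: a Grade 3 event starting on Day 25 needs 7 more days, to Day 32, before it can be judged. This stands as the sensible reading, and it defeats the inference that a haematological DLT could never be counted. It does not make Sections 6.1.5 or 9.2 wait for Day 42.

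Second, the 4-week trigger is written only for the first three patients, and its use for patients 4-6 is inferred. That is correct. Four weeks is also a minimum, and the Data Review Team could have waited longer.

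Third, several provisions make it plausible that slow recovery was seen:
- Section 4.1 allows venetoclax and APR-246 to be held from Day 29, with Cycle 2 azacitidine also delayed, until ANC recovers in patients on venetoclax plus azacitidine who are in CRi or MLFS. This covers neither platelets nor Cohort 1.
- Section 7.1 (footnote k) and Section 7.2.2.4 provide a repeat marrow at about Day 35, with Medical Monitor discussion, for hypocellular patients whose venetoclax is held.
- Sections 6.1.5 and 8.1.2.7 have all accumulated safety data discussed at the meetings, and 8.1.2.7 provides for summaries or minutes. Those records may settle the question, but they are not in the documents.

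None of these extends the DLT period or covers every cytopenic patient.

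**Conclusion.** The point holds as a minor defect in a primary-endpoint rule. Followed as written, the rules allow a patient to be counted DLT-free, and the RP2D to be declared, up to 14 days before the only haematological criterion can be judged. The open question is limited to patients 4-6 of each lead-in cohort, six of 12 patients, and to those among them who started within the dates shown.

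A reader might infer that a DLT was missed, that 0 of 6 is false, or that 4.5 g/day is the wrong dose. The documents support none of these. One or more cycles of treatment is compatible with Day 42 having been known for everyone, and no haematological DLT rate is given from which a chance of reversal could be calculated. Both lead-in cohorts are closed, so the practical effect is confined to the reported DLT count and any further dose decision.

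Confidence is high that the rule is missing. There is no basis for a claim about the effect on the count.

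**What to change.** **1. Wording**, in 4.1, 6.1.4, 6.1.5, 9.2, 9.3.1 and the synopsis:
- Cytopenia with onset in Cycle 1 is followed to Day 42. It is a DLT if ANC or platelets have not recovered to the stated thresholds by then in the absence of active leukemia or myelodysplasia.
- A patient with unresolved cytopenia is not DLT-evaluable as DLT-free until Day 42, or recovery if sooner. No further RP2D or dose decision is final until then.

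**2. Reporting.** In the final DLT analysis, apply this definition to all 12 lead-in patients, using the weekly counts (7.1, footnote l), the Day 22 marrow and any Day 35 repeat. Show the resulting DLT count and RP2D beside the Data Review Team's original conclusion, labelled as a later clarification.

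The data are already scheduled. If Cycle 2 starts on Day 29, its Day 1, 8 and 15 counts fall on study Days 29, 36 and 43, and weekly counts cover a delayed Cycle 2. The Day 8 and Day 15 visits have ±3-day windows, so show the actual count dates. Note also that counts taken after an on-time Cycle 2 start may reflect Cycle 2 dosing.

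**Cost.** Edits in six places and one 12-patient table; up to 14 days' delay for any further dose decision while cytopenia is unresolved; and possibly a less favourable DLT count.
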